25% based on a previously conducted pilot study), (3) number of case/control periods, and (4) proportion of participants who are statistically informative (with both case and control periods). Given the transient nature of flares, in our view, only activity exposures with moderate magnitude effects (ORs of 1.5-2.0) will have a meaningful impact on the population level. Informed by the characteristics of activities, flares, and missing data from our pilot, we estimated power using simulated data with 1000 replications, assuming  $\alpha=0.005$  (Bonferroni-corrected for 10 activity groups), comparing different assumptions for sample size determinants, including activity frequencies as low as 3%. A sample size of  $n=440$  yielded  $\approx 90\%$  power to detect ORs of 1.5 for activity frequencies  $\approx 10\%$ , 80% power to detect OR=1.6 at activity frequency=5%, and 80% power for OR= 1.81 given activity frequencies as low as 3% (**Figure 2**). Allowing for 40% of participants not being analyzed due to having limited data available (loss to follow-up, fail run-in period, etc.), this yielded **a planned sample size of  $n=730$  for Aim 1**. These power estimates are highly conservative, since (1) they use data from scheduled e-Questionnaires only and assume no data from *ad hoc* flare-window e-Questionnaires, and (2) they assume no information at all from the  $n=290$  with limited data. Moreover, they are based on binary activity exposures, and analyses using continuous exposures (incorporating duration and frequency) will have greater power. As a point of comparison, the previously conducted pilot study was able to detect ORs  $\geq 2.5$  and  $p$ -values  $< 0.001$  despite having  $\sim 9x$  fewer participants than the currently proposed study. For Aim 2, using the same data simulated for Aim 1, and assuming an expected mean (standard deviation) 1-year RMDQ scores of 8.8 (6.4) from a prior study, Bonferroni-corrected  $\alpha=0.005$ , activity frequencies  $\approx 20\%$ , and  $n=440$  without missing data (from  $n=730$  initially recruited), we estimated power over a range of scenarios where we varied the strength of the association between the *change* in activity frequency over the 1st 4 weeks of follow-up (for each of the 10 activity categories) and a minimum clinically important change in 1-year RMDQ of 2.5 points. We found  $\geq 80\%$  power to detect a 2.5-RMDQ-point difference at 12 months in scenarios where a 65% change in activity frequency over the 1st 4 weeks produced a 2.5-RMDQ-point difference at 12 months, and in all scenarios where the activity frequency-RMDQ relationships was *more* extreme (e.g., if a smaller % change in activity frequency produced a 2.5-RMDQ-point difference at 12 months. This confirms adequate power with **a planned sample size of  $n=730$  for Aim 2**.

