**5.6.2 a. Aim 1 analyses:** We will examine associations between activity group exposures and the participant-reported flares outcome in conditional logistic regression models, using data from all scheduled and flare window e-Questionnaires over 1- year. There will be one model for each of the 10 primary activity categories. Models will include activity categories as time-varying predictors as in **equation 1**, where  $Y$  is the outcome (flare vs. no flare),  $x$  is the activity

exposure (yes vs. no), and  $C$  represents potential time-varying confounders (psychological factors, other activities). The letter  $i$  indicates the  $i^{\text{th}}$  individual ( $i = 1, 2, \dots, n$ ),  $j$  indicates the  $j^{\text{th}}$  time of follow-up ( $j = 1, 2, \dots, n_i$ ) and  $x_{i(j-1)}$  indicates an activity that was performed in the exposure window prior to the  $j^{\text{th}}$  time (either the start of the control window [scheduled e-Questionnaire] or time of flare onset [flare window e-Questionnaire]). As previously noted, the survey methods are such that activity exposure and flare outcome are inherently time-lagged, with exposure preceding outcome.  $\beta_w$  represents the association of activity  $x$  with flare outcome  $Y$  within individuals (the ‘within-individual effect’), or the expected odds of a flare with change in the activity exposure for a given individual. These analyses will yield odds ratios (OR) and 95% confidence intervals for within-individual ‘effects’ of activity triggers on an LBP flare. The initial analytic approach (**Figure 3**) will examine the association between binary activity exposure and binary flare outcome, with explicit adjustment for pain NRS and number of prior flares measured at time= $j-1$ , and time-variant confounders selected based on conceptual importance; *by design*, the case-crossover method uses each person as their own control, accounting for known and unknown confounds that are fixed or relatively stable over time (i.e., age, sex, sociodemographics, medical and LBP history, work-related factors, and underlying psychological predispositions). We will use a Bonferroni-corrected threshold of  $p=0.005$  for each

$$\log \left[ \frac{Pr(Y_{ij} = 1)}{1 - Pr(Y_{ij} = 1)} \right] = \beta_{0i} + \beta_w x_{i(j-1)} + \gamma C_{i(j-1)}, i = 1, 2, \dots, n; j = 1, 2, \dots, n_i \quad (1)$$

[figure not shown]

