\*Analysis includes all scheduled and flare window e-Surveys. Activity exposures over prior 24-hr and 2-hr effect periods, and current flare status, are inherently time-lagged.

primary activity-

flare comparison to account for 10 statistical comparisons (one for each of the 10 activity categories). We will further examine for activity-flare associations after accounting for important relationships based on theory and clinical knowledge, including the following: dose-response relationships; work- specific activity-flare associations; multivariate analyses including other potential confounders (other time-varying activities, depression, PTSD, stress, catastrophizing); potential moderators; different effect-periods of activity exposures (i.e., 24 vs. 2 hours); possible biases (e.g., conscious activity avoidance and carry-over effects); and clinical subgroup analyses (lumbosacral radicular syndrome [LSRS] symptomatic lumbar spinal stenosis [SLSS] diagnosed by a specialist, ascertained by chart review). We will also conduct similar subgroup analyses as secondary analyses, targeting the expanded target population subgroups described above (facet-mediated pain, SIJ-mediated pain, spondylolysis, ascertained by EHR review). We will analyze the reliability and accuracy of these subgroups. Of note, the primary analysis of walking, standing, and sitting will use the ActiGraph data (which are only obtained for the 1st 4 weeks of follow-up); secondary analyses will use the self- reported data for these 3 groups over the entire 1-year follow-up, and will also examine the association between ActiGraph and self-reported data. After these analyses using the binary flare outcome, we will use an analogous approach to examine relationships between activity categories and the secondary (continuous) outcome of NRS LBP intensity, with linear mixed-effects regression. These analyses account for potential biases that might be introduced by participant self-identification of flare status; if no such bias exists, we would expect the direction of effects to be similar to those obtained in the initial analysis of flares.

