**5.6.2b. Aim 2 analyses:** We will examine associations between the frequency of activity during scheduled e-Questionnaires (% of periods during which each of the 10 primary activity categories were reported over the 1st 4 weeks of follow-up), and the outcome of long-term LBP-related functional limitations at 12 months as reflected by the RMDQ, using a Bonferroni-corrected threshold of p=0.005 (**Figure 4**). Activity over the 1st 4 weeks is the exposure of interest for the Aim 2 analysis because activity restriction is most expected early in an episode of LBP, and because of our previously-stated reasoning that early changes in activity may be particularly important in determining long-term/overall activity-function relationships. The percentage of periods with each activity category over the 1st 4 weeks will be calculated from self-reported activity information and ActiGraph output. The main multivariate model for each activity category will explicitly adjust for a range of potential confounders based on prior knowledge and conceptual rationale, including baseline RMDQ score, and all psychological predictors and other baseline covariates. We will then conduct secondary analyses analogous to that done for Aim 1 to examine activity-1-year-RMDQ associations after accounting for important relationships based on theory and prior knowledge: potential moderation by baseline employment status, compensation status, or job satisfaction; potential moderation by analgesic use over the first 4 weeks of follow-up; sensitivity analyses contrasting associations with cumulative activity exposure early (weeks 1-2) vs. late (weeks 3-4 or weeks 5-8).

during follow-up; and clinical subgroup analyses (LSRS and SLSS subgroups). We will use the same approach for the secondary outcomes of LBP intensity, lost work productivity, quality of life, and analgesic use at 1-years.

Analyses for Aims 1 and 2 will use VA administrative data to weight the sample of participants back to represent the target population of Veterans with back pain (including those who did not respond to the study).

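### Each aim holds its ten activity tests to a fixed Bonferroni 0.005; Holm's step-down keeps the same 5% family-wise bound, rejects everything Bonferroni rejects, and gains modest power if several activities have effects

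*Combined protocol and SAP*

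**What the plan says.** For Aim 1, section 5.6.2a specifies separate models: "There will be one model for each of the 10 primary activity categories". It then says "We will use a Bonferroni-corrected threshold of" p=0.005 for each primary activity–flare comparison, "to account for 10 statistical comparisons (one for each of the 10 activity categories"). For Aim 2, section 5.6.2b relates activity frequency in the first four weeks to the 12-month RMDQ, "using a Bonferroni-corrected threshold of p=0.005".

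The power work in 5.6.1 uses the same level, described as "Bonferroni-corrected for 10 activity groups". With 440 analysable participants it reports, among other figures, "80% power to detect OR=1.6 at activity frequency=5"%.

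No step-down procedure is mentioned, and no reason is given for a single-step rule. Section 5.6.2a plans 95% confidence intervals for the odds ratios. Section 5.6.2 describes the analytic approaches as preliminary and open to change.

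**The concern.** Under the fixed rule, each activity must reach 0.005 whatever the other nine tests show. The bound on any false claim is spread over ten hypotheses even after some have been rejected and can no longer contribute a false positive. Holm's procedure reuses that allowance. It compares the smallest p-value with 0.05/10, the next with 0.05/9, and so on, stopping at the first failure.

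Sections 3.0 and 5.6.3 promise tables covering all ten activities for both short-term and long-term effects. Missing real effects on some activities is therefore relevant to the product, even when others are found. What is at stake is some power for the second and later discoveries. The validity of the analysis is not in question.

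**Working it through.** **Inputs.** Ten tests per aim, one p-value per activity, threshold 0.005 (5.6.2a and 5.6.2b). Power of 80% per activity at 0.005 (5.6.1: OR 1.6 at 5% activity frequency, and OR 1.81 at 3%). Section 5.6.1 also gives about 90% for OR 1.5 at about 10% frequency.

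**The plan's own figure.** 0.05/10 = 0.005 reproduces exactly. The 5% family level is implied rather than written. The power figures come from the study team's simulation. Its flare rate, number of periods and within-person correlation are not given, so those figures are taken as stated.

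**Holm thresholds**, 0.05/(10 − k) after k rejections: 0.0050, 0.0056, 0.0063, 0.0071, 0.0083, 0.0100, 0.0125, 0.0167, 0.0250, 0.0500. None is below 0.005, so no Bonferroni rejection can be lost.

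**Error control.** Suppose m of the ten null hypotheses are true. When Holm first reaches one of them, at most 10 − m hypotheses have already been rejected, so the threshold is at most 0.05/m. The chance that any of the m p-values falls below 0.05/m is at most m × 0.05/m = 0.05, whatever the correlation between activities.

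**Power at each step.** An effect with 80% power at 0.005 (two-sided) has 80.9% power at the threshold in force after one rejection, 84.4% after four and 95.4% after nine.

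**Simulation.** Ten two-sided z-tests, 100,000 replications, each true effect set to 80% power at 0.005. Average power per true effect, Bonferroni to Holm:

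| True effects | Independent | Correlation 0.5 |
|---|---|---|
| 1 | 80.1% to 80.1% | 80.2% to 80.2% |
| 2 | 80.2% to 81.0% | 80.0% to 80.7% |
| 3 | 80.1% to 81.7% | 80.0% to 81.4% |
| 5 | 80.0% to 83.6% | 80.0% to 83.0% |
| 7 | 80.0% to 86.1% | not run |
| 8 | 80.1% to 87.8% | 80.0% to 86.2% |
| 10 | 80.0% to 92.7% | 80.0% to 89.6% |

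Starting from 90% power with independent tests, Holm gives 91.1% with three true effects and 92.5% with five.

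The chance of finding at least one true effect is essentially the same under both rules, because the first step is identical. With three true effects and independent tests it is 99.2% under both.

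The chance of finding every true effect moves more. With five independent effects it goes from 33% (0.8^5 = 0.328) to 43%. With seven it goes from 21% (0.8^7 = 0.210) to 39%.

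**What it costs in actual error.** With five true effects and independent tests, five nulls remain. Bonferroni's family-wise error is 1 − 0.995^5 = 2.5% exactly (2.4% to 2.6% across simulation runs), and Holm's is 4.2% to 4.4%. With seven true effects, Bonferroni gives 1 − 0.995^3 = 1.5% and Holm 3.9% to 4.0%. Across all scenarios, including no true effects, Holm reached 4.9% to 5.0%.

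**The case against.** The strongest reply is that this is a choice between two valid procedures. A reader might infer that the fixed rule gives power away for nothing. It does not. Both rules share the 5% bound, but Bonferroni's actual error is lower whenever true effects exist, and Holm buys its power with that unused margin. Section 5.6.3 contemplates advice that an activity be avoided, so a stricter actual error rate is a defensible preference. This objection stands. It makes the change a trade, though one that stays inside the bound the plan itself chose.

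A second tempting reading is that the plan expects many non-null activities, which would make the larger gains the relevant ones. Section 5.6.3 expects short-term and long-term patterns to differ between activities. It does not say how many of the ten have effects in either aim, and one of its examples has no long-term effect. With one to three true effects the gain runs from nil to under 2 points. Section 5.6.1 powers each activity singly, so the chance of finding every true effect is a secondary measure here.

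A third argument is that Bonferroni offers simple matching simultaneous intervals. That is true in general, but those would be 99.5% intervals and 5.6.2a plans 95% ones, so the advantage is not being used. Reported intervals and significance decisions already do not correspond under the current rule, and Holm does not repair that.

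**Conclusion.** This is an optional efficiency gain at low cost; the plan contains no error on this point. Bonferroni at 0.005 is valid, and the power stated in 5.6.1 becomes a lower bound under Holm. The recruitment target of 730 is unaffected.

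From 80% power per true effect, the gain in average power is nil with one true effect, about 1.5 points with three, 3 to 4 with five and 5 to 6 with seven. It is smaller from 90%. These sizes assume two-sided tests (sidedness is not stated), normal test statistics, equal power for every true effect, and a number of true effects that the documents do not give. Holm's 5% bound and its inclusion of every Bonferroni rejection do not depend on those assumptions.

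The 5% bound applies within each aim. Over both aims together it is 20 × 0.005 = 10% under the current rule, and likewise 10% with Holm at 5% in each aim.

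**What to change.** In 5.6.2a and 5.6.2b, replace the fixed 0.005 threshold with Holm's step-down at family-wise 5% within each aim, applied to the ten primary p-values. Report Holm-adjusted p-values: for the k-th smallest, the largest of (10 − j + 1) × p(j) over j = 1 to k, capped at 1. Keep the planned 95% confidence intervals and label them as unadjusted. Keep 0.005 in 5.6.1 as the conservative planning level.

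Make the change before outcome results are examined. Section 5.6.2 leaves the methods open to change with the data at hand, and a later switch to a less strict rule could look data-driven.

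The cost is SAP wording; data, models and sample size stay as they are. There are two small downsides to state in the plan. Actual family-wise error moves closer to 5% when true effects exist, and the unadjusted intervals do not map directly onto the Holm decisions: a 95% interval may exclude the null for an activity that Holm does not declare significant.

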## Overview of the Overall Study Approach

The content of subsequent sections warrants an introduction to the overall approach to the research involved. The research as a whole involves two separate but related components: (1) **a VA component** involving all VA recruitment, VA data collection, and all processes involving VA data (addressed by the current VA IRB application and referred to as the “VA component”), and (2) **a non-VA component** involving non-VA data collection that occurs entirely outside the VA and does not involve any VA data. This means that the current human subjects application and the VA informed consent processes described in this application pertain only to the VA component of the research (the VA research processes). Separate from the VA component of the research is the non-VA component, which will be carried out by researchers at the University of Washington (UW). Participants in the VA component of this research will be provided information that they can use to initiate contact, screening, and possible enrolment in the non-VA component conducted by UW researchers. The non-VA component of the research will run in parallel with the VA research processes, yet involves non-VA data collection only. The UW research processes will undergo a separate process of IRB approval at UW, including a separate process of informed consent. This non-VA data collection will include all e-Questionnaires described above, administered by a private (non-VA) data collection company specializing in secure HIPAA-compliant and 21 CFR 11-compliant electronic questionnaire administration (DatStat). DatStat has a successful track record for conducting secure electronic questionnaire administration for another current UW research study. Acquisition of e-Questionnaire data in this proposed manner- in partnership with UW researchers- permits the ability to conduct frequent serial assessments with quasi-randomized timings via e-Questionnaires, since at the current time there exist no feasible processes to collect such data as VA data using VA devices. At interim time points during the VA component of this study, e-Questionnaire data being collected by UW researchers as part of the non-VA component of this study will be downloaded by VA research study staff involved with this VA research study, at which time such data will become VA data and will not subsequently be shared outside the VA during the study. **In summary, no VA data produced as part of this VA research study will be shared outside of the VA at any point during the conduct of this VA research. However, non-VA data collected by researchers at the UW will be shared with this VA research team.** Thus, the flow of research data in this VA research study is only into the VA, and never out of the VA.

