## 5.1 Study Design

This will be an ***observational***, longitudinal case-crossover study nested within a cohort study, following up to 730 Veterans seen for LBP in VA primary care prospectively for 12 months. Study procedures will not make changes to nor in any way affect the typical medical care for LBP provided at VAPSHCS. **All study assessments following recruitment will be “e-Questionnaires” that participants complete using their own personal electronic devices (smartphones, tablets, or PCs, not provided by the study).** There are two types of e-Questionnaires that participants will complete: “*scheduled e-Questionnaires*” and “*flare window e-Questionnaires*”. Scheduled e-Questionnaires are quasi-random, ‘cue-elicited’ frequent assessments that will be repeated numerous times throughout the 1-year follow-up period. Cues to complete scheduled e-Questionnaires are automated “e-Alert” notifications sent by text message and email at the start of each “*scheduled assessment window*”, the 3-hour period during which a scheduled e-Questionnaire may be completed. ***Scheduled e-Questionnaires will occur three times each week during weeks 1-4 of follow-up, once a week during weeks 5-8, and twice a month during months 2-12.*** Participants will also complete unscheduled “*flare window e-Questionnaires*” on an *ad hoc* basis, if they experience new flares of LBP at any time during the 1-year follow-up period. At study entry, participants will receive training on how to complete flare window e-Questionnaires, if they experience flares of pain, by logging on to a secure Participant Portal (the **Flares of LBP with Activity Research Study** or “FLARES” website) within 3 hours after the onset of a new pain flare. In addition, all scheduled e-Questionnaires will remind participants to complete a flare window e-Questionnaire if they have a new pain flare. Scheduled e-Questionnaires and flare window e-Questionnaires generally contain the same question items, however, scheduled e-Questionnaires inquire about activity exposures *preceding the start of the scheduled assessment window* (when e-Alert notifications are sent), and flare window e-Questionnaires inquire about activity exposures *over the time period preceding the flare onset*. Each e-Questionnaire will begin by prompting the participant with the definition of a LBP flare. Participants will then report whether or not they are experiencing a flare, the primary outcome for Aim 1 of this study. E-Questionnaires will also inquire about activity exposures that have occurred over the 24-hour period prior to the assessment window start and - *if* an activity is reported – ask for further clarification of whether the activity was performed in the 2-hour period prior to the assessment window start. Further questions included in every e-Questionnaire are time-varying pain and psychological covariates (pain intensity, depression, catastrophizing, stress, etc.) assessed using brief, validated measures. All e-Questionnaires are inherently time lagged for activity-flare relationships, since they capture *current* flare status at time=t, and activities in the 24-hour period *before* the start of the assessment window/flare onset (t-1). Participants may also be offered to wear the optional ActiGraph wGT3X-BT unit continuously for weeks 1-4 of the study. Due to the participant burden involved with frequent serial e-Questionnaire assessments, a run-in period during weeks 1 and 2 of follow-up will exclude those individuals unable to maintain compliance with these assessments. Aim 1 analyses will examine the short-term effects of 10 specific activity categories on participant-reported flares across all study assessments over 1-year follow-up. Aim 2 analyses will examine associations between the frequency of exposure to 10 specific activity categories over weeks 1-4 of follow-up, and long-term functional recovery at 12 months as defined by the RMDQ. All analyses will use a biopsychosocial framework accounting for potential confounders (sociodemographics, psychological factors, etc.) and effect modifiers, and will include sensitivity analyses to examine the robustness of findings and important study assumptions.

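### The 2-hour Aim 1 odds ratios compare exposure windows tied to different clock times with no clock-time term, so they can be biased in either direction

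*Combined protocol and SAP*

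**What the plan says.** Section 5.1 (Study Design) sets two look-back periods. The longer one is given as "E-Questionnaires will also inquire about activity exposures that have occurred over the 24-hour period prior to the assessment window start". For each item that the participant endorses, a follow-up question will "ask for further clarification of whether the activity was performed in the 2-hour period prior to the assessment window start". Flare-window reports ask about the time before flare onset instead.

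The anchors therefore differ. Section 5.6.2a defines the end of the exposure window as "either the start of the control window [scheduled e-Questionnaire] or time of flare onset [flare window e-Questionnaire". Scheduled alerts are sent by the study; the Overview in section 3.0 describes "frequent serial assessments with quasi-randomized timings via e-Questionnaires", and the permitted clock hours are not given. Flare-window reports are started by the participant, "within 3 hours after the onset of a new pain flare".

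Section 5.6.2a fits conditional logistic models "using data from all scheduled and flare window e-Questionnaires over 1- year". The adjustments it names are pain NRS, number of prior flares, psychological factors and other activities, with further time-varying confounders to be chosen on conceptual grounds. The biases it names, as examples, are activity avoidance and carry-over. Clock time appears in neither list. The comparison of "different effect-periods of activity exposures (i.e., 24 vs. 2 hours" stands among the further Aim 1 analyses.

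**The concern.** Whether someone lifted, bent or sat in the previous 2 hours depends strongly on the hour of day. Two hours before a flare noticed on waking are mostly sleep; two hours before a mid-afternoon alert are not. A 24-hour window takes in a full daily cycle wherever it ends, so this difference largely cancels. Over 2 hours it does not.

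Section 5.6.2a credits the case-crossover design with removing factors that are fixed or relatively stable over time. Hour of day varies within a person, so it is not among them.

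At stake are the 2-hour ORs and the reading of the 24-hour against the 2-hour result. A difference between the two could be taken as evidence on how quickly an activity acts when part of it is time of day. The plan regards ORs of 1.5 to 2.0 as the meaningful range (section 5.6.1), so a distortion of a few tenths matters.

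**Working it through.** The documents give no figure for this point. The Aim 1 sample size is not affected by it: 440/(1 − 0.40) = 733, against 730 planned.

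**Assumed inputs** (none is in the documents)
- 2-hour exposure prevalence is 15% in the hours when alerts are sent and 3% outside them.
- No alerts fall outside those hours.
- A share q of flare-window onsets falls outside them: 10, 20, 30 or 50%.
- A share s of all cases comes from flare-window reports: 1 or 0.5. The remaining cases are flares reported on scheduled questionnaires, which use the alert clock.

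**Formulas**
- Share of all case windows outside alert hours: s × q.
- Case exposure in a stratum with prevalence p and true OR θ: θp/(θp + 1 − p).
- Overall case exposure: (1 − sq) × (value in alert hours) + sq × (value outside).
- Observed OR: odds(overall case exposure)/odds(0.15), where odds(0.15) = 0.1765.

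**Null activity, q = 30%**
- s = 1: 0.70 × 0.15 + 0.30 × 0.03 = 0.114; odds 0.1287; OR 0.73.
- s = 0.5: 0.85 × 0.15 + 0.15 × 0.03 = 0.132; odds 0.1521; OR 0.86.

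**True OR 1.5, q = 30%.** Stratum case exposures are 0.225/1.075 = 0.2093 and 0.045/1.015 = 0.0443.
- s = 1: 0.70 × 0.2093 + 0.30 × 0.0443 = 0.1598; odds 0.1902; OR 1.08.
- s = 0.5: 0.85 × 0.2093 + 0.15 × 0.0443 = 0.1846; odds 0.2263; OR 1.28.

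| q | Null, s = 1 | Null, s = 0.5 | True 1.5, s = 1 | True 1.5, s = 0.5 |
|---|---|---|---|---|
| 10% | 0.91 | 0.95 | 1.35 | 1.43 |
| 20% | 0.82 | 0.91 | 1.21 | 1.35 |
| 30% | 0.73 | 0.86 | 1.08 | 1.28 |
| 50% | 0.56 | 0.77 | 0.82 | 1.14 |

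With a weaker rhythm (10% against 5%) and s = 1, the null OR runs from 0.94 at q = 10% to 0.73 at q = 50%.

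**Only the gap between the two clock distributions matters.** Suppose 10% of alerts also fall in low-activity hours, with q = 30% and s = 0.5. Control exposure is 0.90 × 0.15 + 0.10 × 0.03 = 0.138. The share of cases outside is 0.5 × 30% + 0.5 × 10% = 20%, so null case exposure is 0.126. The OR is 0.1442/0.1601 = 0.90.

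**Reverse mismatch.** Let prevalence be 10% in active hours and zero in inactive hours, with all onsets in active hours and a share g of alerts in inactive hours. Then OR = odds(0.10)/odds((1 − g) × 0.10), which is 1.12, 1.28 and 1.48 for g = 10, 20 and 30%. A null activity now looks like a trigger.

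**Effect of adjustment.** A small simulated conditional logistic analysis had 440 people, about 3 flares each, every case a flare-window report, and 30% of flares against 3% of alerts at inactive hours. Adding clock-time terms moved the mean OR from 0.69 to 0.94 when the truth is 1.0, and from 1.01 to 1.41 when it is 1.5. Five runs per setting are too few to say whether the remaining gap is chance.

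**The case against.** Four points on the other side have weight.

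- **Not every case is misaligned.** Each questionnaire, scheduled ones included, asks about current flare status (section 5.1), and the power calculation uses scheduled reports only (section 5.6.1). Flares reported there share the alert clock with the controls. This stands, and it is why the table has s = 0.5 columns; the real share is not given.
- **The 2-hour window is not the natural primary.** It is listed among further analyses, and Aim 1 is framed as effects within 24 hours (section 3.0). The documents do not plainly name the primary window, but on that reading the ten Bonferroni-tested comparisons are largely untouched.
- **The plan leaves room.** Open wording on time-varying confounders and a non-exhaustive list of biases would allow a clock-time term. They do not commit to one. The planned pain NRS analysis addresses self-identification of flares, not window timing.
- **The inputs are guesses.** Neither clock distribution is known. The 3-hour reporting rule limits reports of overnight onsets, though not of flares noticed on waking, and makes the larger values of q less plausible.

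A reader might infer that null activities will look protective and real triggers will be hidden. The documents do not support that: it needs onsets to fall more often than alerts in low-activity hours, and the reverse mismatch creates false triggers. Nor does "if they experience new flares of LBP at any time during the 1-year follow-up period" establish night-time onsets; it describes coverage of the follow-up year, not hours of the day. Likewise, it cannot be said that no scheduled window looks back into sleep, because alert hours are not stated.

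**Conclusion.** The point holds for the 2-hour analyses. Case and control windows have different clock anchors, both report types are pooled, the design does not remove time of day, and no adjustment is planned. If alerts and onsets are distributed differently over the day, the 2-hour OR and its comparison with the 24-hour OR are biased.

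The direction is unknown: towards or below 1 if onsets fall more often in low-activity hours, above 1 in the reverse case. Under the assumptions above, and with 30% of flare-window onsets outside alert hours, a null OR of 0.73 to 0.86 and a true 1.5 seen as 1.08 to 1.28 show a plausible scale, not an estimate. The apparent reversal of a true trigger (0.82 at q = 50%) requires every case to be a flare-window report; with half of them it is 1.14.

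It would go too far to say that the 24-hour Aim 1 results are compromised. The change is worth making before analysis because it is cheap and does not depend on guessing the direction.

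**What to change.** In section 5.6.2a, for the 2-hour models only:

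1. Add the clock-time band of the window end, for example in 4-hour bands. Use alert time for scheduled reports and reported onset time for flare-window reports. The documents do not say that onset clock time is recorded. If it is not, use the report time, due within 3 hours of onset, as a proxy and state that it is approximate.
2. State the hours in which alerts are sent, and show the clock-time distributions of alerts and flare onsets.
3. Report the 2-hour OR with and without the adjustment before comparing it with the 24-hour OR.
4. Make restriction to flares with onset in alert hours a sensitivity analysis, not the main comparison, and give the number of flares it drops. Under the illustration that is 10 to 50% of flare-window flares, which is not small.

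The cost is a few extra model terms and slightly wider intervals in the 2-hour analysis, with no change to sample size. One practical limit applies: in a band with onsets but no alerts, the band term cannot be estimated and those flares carry no information on the activity. Such flares should be counted and reported.
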